### 1.5. Risks and Benefits

TD-1473 is being evaluated for the treatment of inflammatory intestinal disorders. Treatment with tofacitinib, a systemic pan-JAK inhibitor, has demonstrated to result in statistically significantly higher rates of remission compared to placebo. However, given limited data from the Phase 1b Study in a small number of subjects with moderately-to-severely active UC treated with TD-1473 for 4 weeks, efficacy with TD-1473 in UC has not been established.

Some patients receiving repeated doses of tofacitinib, a systemic JAK inhibitor, have exhibited alterations in cholesterol (LDL, HDL, and total cholesterol), liver function tests, serum creatinine, decreased red blood cell and white blood cell (particularly neutrophils and lymphocytes) counts, infection (particularly herpes zoster and tuberculosis), cancer (including lymphoma), intestinal perforation, and thromboembolic events. In addition to these, diarrhea and rash have also been reported. However, given the anticipated relatively low systemic exposure of TD-1473, these risks are anticipated to be minimal in the current study.

In the Phase 1 Study in healthy volunteers, all treatment-emergent adverse events (TEAEs) in subjects dosed with TD-1473 (most commonly noted were headaches at 100 mg and 300 mg with similar or lower prevalence as placebo) were mild in severity and short in duration. In the Phase 1b Study in UC subjects, TD-1473 was generally well tolerated with only two adverse events (urticaria at 80 mg and papular rash at 20 mg) deemed by the Principal Investigator (PI) to be possibly related to study drug; the adverse events were considered mild in severity, in both cases and resolved within a few days after the last dose of study drug. No adverse event led to drug interruption or discontinuation. Similar to the healthy volunteer study, there were no adverse alterations in vital signs, electrocardiogram parameters, or laboratory evaluations relative to placebo. There have been additional Phase 1 studies in healthy volunteers that, together, have not yielded a repeated pattern of TEAEs frequently observed in every study.

The potential risks described in this section will be carefully assessed during the Study. Assessments include scheduled physical exams, and frequent monitoring of complete blood cell counts with differential, kidney and liver function, creatinine phosphokinase, and fasting cholesterol panel.

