**Coexisting medical conditions or past medical history:**

6. Deemed by the investigator to be inappropriate for this study; or has any condition which would confound or interfere with the evaluation of the safety or tolerability of the study drug [e.g., developed unstable or uncontrolled and clinically significant allergic (except for untreated, asymptomatic, seasonal allergies), hematological, endocrine/metabolic, coagulation, immunologic, pulmonary, cardiovascular, hepatic (except hepatic steatohepatitis), GI (except UC), genitourinary, psychiatric, oncologic thrombotic (e.g., deep vein thromboses (DVT) or pulmonary embolism or neurological disease or other medical disorder before during or after Protocol 0157)]; or is unable or unwilling to comply with the study protocol.
7. Develops hypersensitivity to excipients or contents of the study drug as noted in Protocol 0157.
8. Participating in or interested in participating in another investigational study (exception Protocol 0157)
9. Has clinically significant abnormalities in the results of laboratory evaluations at the most recent laboratory evaluation prior to LTS Day 1 visit as determined by the investigator, including:
  - AST, ALT, or alkaline phosphatase  $\geq 2x$  the upper limit of normal (ULN)
  - Total bilirubin  $> 2x$  ULN (unless diagnosis of Gilbert's syndrome)
  - Creatinine clearance as calculated by the Cockcroft-Gault formula  $< 30$  mL/min (Refer to [Appendix 2](#))
  - Total white blood cell count (WBC)  $< 3 \times 10^9/L$
  - Absolute neutrophil count  $< 1.5 \times 10^9/L$
  - Absolute lymphocyte count  $< 0.8 \times 10^9/L$
  - Hemoglobin  $< 8$  g/dL
  - Platelet count  $< 100 \times 10^9/L$ .
10. Subject has had a live viral vaccine (e.g., MMR, varicella zoster, herpes zoster, oral polio virus, FluMist®, attenuated typhoid fever vaccine, attenuated rotavirus vaccine, yellow fever vaccine, or any investigational live vaccine) within 4 weeks prior to Day 1 and/or is unwilling or unable to avoid live viral vaccines during the Study and for 8 weeks following the last dose of study drug. Subject must be willing to avoid contact with any

household member who has been vaccinated with a live attenuated vaccine within 2 weeks after vaccination.

11. Are pregnant, lactating, breastfeeding or planning to become pregnant during the Study or within 7 days after the last dose of Study Drug

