## 7.2. Clinical Laboratory Abnormalities and Other Abnormal Assessments as Adverse Events or Serious Adverse Events

Abnormal laboratory findings (such as clinical chemistry, hematology, or urinalysis) or other abnormal assessments (such as electrocardiograms [ECGs], X-rays, or vital signs) that are associated with signs and/or symptoms or are considered clinically significant in the judgment of the investigator must be recorded as AEs or SAEs if they meet the definition of an adverse event (or serious adverse event), as described in Section 7.1.1 (Adverse Event) and Section 7.1.2 (Serious Adverse Event).

Clinical laboratory abnormalities of concern may include, but are not limited to, the following where the investigator must recheck within 2-7 days, except for AST or ALT > 3x ULN where these need to be rechecked within 48-72 hours, as deemed appropriate by the investigator:

- clinically significant reduction in neutrophils or leukocytes or lymphocytes that may place subjects at higher risk for infection such as:
  - moderate or severe neutropenia (e.g., absolute neutrophil count of < 1.0 x 10^9/L)
  - moderate or severe leukopenia (e.g., white blood cell count of < 2.0 x 10^9/L)
  - moderate or severe lymphocytopenia (e.g., absolute lymphocyte count of < 0.5 x 10^9/L)
- abnormal hepatic panel (AST or ALT > 3x ULN)
- an excessive decrease in creatinine clearance [e.g., a reduction by ≥ 50% from baseline (baseline for this purpose is defined as creatinine clearance calculated for Day 1, predose activities)]

Depending on the subject's baseline and individual scenario, the investigator should report as an AESI and stop study drug treatment if any of the below is seen:

- moderate or severe neutropenia (e.g., absolute neutrophil count of < 1.0 x 10^9/L) on two sequential laboratory reports
- moderate or severe leukopenia (e.g., white blood cell count of < 2.0 x 10^9/L) on two sequential laboratory reports
- moderate or severe lymphocytopenia (e.g., absolute lymphocyte count of < 0.5 x 10^9/L) on two sequential laboratory reports
- a reduction by ≥ 50% from baseline in creatinine clearance on two sequential laboratory reports
- ALT or AST > 8x ULN on a single laboratory report. Note: See [Appendix 6](#) for an algorithm of evaluating and managing subjects with ALT or AST > 3x ULN.

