### **8.6.3. Laboratory Data**

Safety laboratory values and C-reactive protein values, changes from baseline, values relative to normal ranges, and clinical laboratory abnormalities of concern will be summarized by visit, overall and by arm. C-reactive protein, [REDACTED] total cholesterol, LDL, HDL, and triglycerides levels will be log-transformed for summarization.

Reference ranges provided by the laboratory for each test will be used to evaluate the clinical significance of laboratory test results. Values falling outside the relevant reference range will be flagged, as appropriate, in the data listings. Clinical laboratory abnormalities of concern will be listed in a separate listing. A listing of pregnancy test results will be provided.

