3.4. Safety Analyses

The analysis of safety data includes an overall summary of adverse event preferred terms by body/organ system, drug exposure (duration of treatment), dosing information/compliance, clinical laboratory results, vital signs and ECGs. Tables summarizing the adverse events reported by subjects who died, experienced non-fatal serious adverse events (SAE), or prematurely discontinued the study due to adverse event (AEs) will be prepared. Summaries of potentially clinically notable laboratory results and vital sign abnormalities are presented.

Inferential statistical tests will not be performed for adverse event incidence rates.

For all safety analyses, the safety analysis population will be used.

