3.4.3. Additional Safety Assessments

3.4.3.1. Clinical Laboratory Parameters

Laboratory data, hematology, serum chemistry and urinalysis, will be summarized in terms of observed values and changes from baseline. In addition, changes from baseline relative to normal ranges from the central lab (e.g., shifts from normal to abnormal high/low) will be summarized.

The number and percentage of subjects with clinically abnormal lab values will also be summarized by timepoint for the following criteria:

- absolute neutrophil count of $< 1.0 \times 10^9/L$

- white blood cell count of $< 2.0 \times 10^9/L$
- absolute lymphocyte count of $< 0.5 \times 10^9/L$

A listing of all abnormal lab values will be provided.

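### SAP 3.4.3.1 counts three of the five laboratory abnormalities named in protocol 7.2, omits AST/ALT and creatinine clearance without declaring it, and its visit rules can undercount those it keeps

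*SAP*

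**What the plan says.** Protocol 8.6.3 plans that safety laboratory values, "changes from baseline, values relative to normal ranges, and clinical laboratory abnormalities of concern will be summarized by visit, overall and by arm". The abnormalities of concern are thus a separate item from values relative to normal ranges. Protocol 8.6.1.1 refers the term to section 7.2. That section gives, as examples, three low blood counts, "abnormal hepatic panel (AST or ALT > 3x ULN"), and a fall of at least 50% in creatinine clearance, where "baseline for this purpose is defined as creatinine clearance calculated for Day 1, predose activities".

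SAP 3.4.3.1 summarises observed chemistry and haematology values and changes from baseline, and adds that "changes from baseline relative to normal ranges from the central lab (e.g., shifts from normal to abnormal high/low) will be summarized". It continues: "The number and percentage of subjects with clinically abnormal lab values will also be summarized by timepoint for the following criteria". The criteria that follow are neutrophils below 1.0, white cells below 2.0 and lymphocytes below 0.5 (× 10⁹/L), and nothing else. SAP 3.4 states more generally: "Summaries of potentially clinically notable laboratory results and vital sign abnormalities are presented".

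Three rules decide which results enter a summary:
- SAP 3.1 admits only scheduled or windowed visits unless noted otherwise.
- SAP 3.1.3 takes the visit from the CRF.
- SAP 3.1.4 keeps the latest laboratory result at a visit, giving repeat testing of abnormal results as its reason.

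Protocol 8.1 undertakes that departures from its planned analyses will be set out in the SAP. SAP Appendix 1 mentions only the efficacy analyses.

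**The concern.** Safety is the primary objective, and the synoptic report will contain no efficacy results. Protocol 1.5 lists liver tests and serum creatinine among the changes seen with a systemic JAK inhibitor, and answers that risk with "frequent monitoring of complete blood cell counts with differential, kidney and liver function, creatinine phosphokinase, and fasting cholesterol panel". Kidney and liver function are thus among the effects the study set out to watch.

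Followed as written, the SAP gives threshold counts for blood cells only. A reader of the report could not see how many subjects in each dose group had AST or ALT above 3 × ULN, or lost half their creatinine clearance. Elsewhere the SAP marks dropped content as not applicable to the synoptic report; here there is no such note. The report would therefore give no sign that a planned safety summary had been narrowed. The visit rules add a second, smaller problem: even the counts that are kept may miss subjects who crossed a threshold.

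**Working it through.** **1. Coverage.** The examples in protocol 7.2 set against the criteria in SAP 3.4.3.1:

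| Protocol 7.2 example | Count in SAP 3.4.3.1 |
|---|---|
| Neutrophils < 1.0 × 10⁹/L | Yes |
| White cells < 2.0 × 10⁹/L | Yes |
| Lymphocytes < 0.5 × 10⁹/L | Yes |
| AST or ALT > 3 × ULN | No |
| Creatinine clearance fall ≥ 50% | No |

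Named 5, counted 3, missing 5 − 3 = 2. The readable SAP text mentions neither AST, ALT, ULN nor creatinine.

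**2. Do other outputs give the missing counts?**

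*Shift tables, liver.* Shifts are against the normal range. Exclusion 9 bars "AST, ALT, or alkaline phosphatase" only from 2 × ULN, so a subject may enter at 1.5 × ULN. A rise to 4 × ULN is then high to high. From a normal baseline, 1.1 × and 4 × ULN fall in one cell.

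*Shift tables, kidney.* Take a woman aged 40, height 162.56 cm, with creatinine rising from 0.5 to 1.0 mg/dL. By protocol Appendix 2:
- Ideal body weight = 45.5 + 2.3 × (162.56 − 152.4)/2.54 = 54.7 kg.
- Clearance before = (140 − 40) × 54.7 × 0.85/(72 × 0.5) = 129.2 mL/min.
- Clearance after = (140 − 40) × 54.7 × 0.85/(72 × 1.0) = 64.6 mL/min, a fall of 50%.

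The documents give no reference range. If the creatinine ULN is 1.0 mg/dL or more, this is normal to normal; if it is 0.9, normal to high. Neither cell identifies the criterion.

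*Minimum and maximum.* The 8-point summary in SAP 3.1 shows the extreme of the selected values, not how many subjects passed a threshold. A creatinine change of +0.5 mg/dL does not settle it either: from 0.5 it is a 50% fall in clearance, but from 1.0, at the same age, it is 1 − 1.0/1.5 = 33%.

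*AESI row (SAP 3.4.2.1).* This counts investigator reports. The list in protocol 7.2 that calls for reporting and stopping drug is mostly stricter: > 8 × ULN once; > 5 × on two reports at least 2 weeks apart; > 3 × twice with raised bilirubin or INR; > 3 × with signs or symptoms of acute liver injury; a clearance fall on two sequential reports. A single symptom-free ALT of 4 × ULN meets the definition of an abnormality of concern but not that list.

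*Listings.* All results are there, but uncounted.

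**3. Visit rules.** Protocol 7.2 asks for a recheck in 2–7 days, or in 48–72 hours for AST/ALT > 3 × ULN. Suppose neutrophils are below 1.0 at Week 12 and at or above 1.0 on recheck:
- Recheck entered under Week 12: the later value is selected and the row shows 0.
- Recheck entered as unscheduled: the first value stays and the row shows 1.
- Low value first found at an unscheduled visit: the row shows 0.

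If a share q of qualifying subjects has a normal recheck under the same visit, the count shows 1 − q of them: of 10 subjects, 10, 5 or 0 for q = 0, 0.5 or 1. The documents do not give q.

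**The case against.** The case for leaving the SAP alone has five parts.

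*The protocol wording is open.* Section 7.2 offers examples without closing the list, and 8.6.3 names no analyte. This stands to the extent that the gap is two of five named examples, not two of five mandatory rows. It does not explain why the SAP reproduces exactly three of those thresholds and stops.

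*Serious cases surface elsewhere.* A reader might infer that marked liver injury would be invisible. The documents do not support that. ALT or AST > 8 × ULN on one report is a criterion for reporting an AESI and stopping drug. It should reach the AESI table and, if drug is stopped for the event, the table of events leading to discontinuation. A confirmed clearance fall has the same route. Section 7.1.4 could even be read as making every 7.2 abnormality an AESI. On any reading, however, the row rests on investigator reporting, which 7.2 ties to the subject's baseline and circumstances.

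*Masking depends on the site.* A reader might infer that most rechecks replace the abnormal value. If visits were assigned by the ±5-day tolerance and visit days were uniform (an assumption), a recheck at 2–3 days would share the window in 17 of 22 combinations (77%), and one at 2–7 days in 39 of 66 (59%). But SAP 3.1.3 follows the CRF visit, so these are not estimates. At present masking can affect only the three haematology threshold counts, because no liver or kidney count exists.

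*The protocol does not promise more.* A reader might infer a commitment to counts at 5 × and 8 × ULN, with bilirubin, or on two consecutive results. Those levels belong to the reporting and stopping rules, not to the by-visit summary.

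*The study stopped early and is reported descriptively.* This limits the consequence. But safety is all that the report covers. The table shells, in a separate document not available here, might contain the rows; the SAP text does not provide for them.

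**Conclusion.** The point holds as a gap between protocol and SAP in the reporting of the primary objective. Two of the five abnormalities named in protocol 7.2 have no laboratory-based count by dose, and the change is not declared. The visit rules can also undercount threshold crossings, including in the three rows that remain.

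What is lost is the summary, not the data, and the other outputs recover part of it. The number of affected subjects cannot be estimated, because the documents give neither laboratory event rates nor the share of rechecks filed under a scheduled visit. The conclusion assumes that the shells add nothing beyond the SAP text. It merits correction because the remedy is small and safety is the report's subject; it does not put the study's safety conclusions in doubt by itself.

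**What to change.** In SAP 3.4.3.1:
- Add two by-timepoint criteria: AST or ALT > 3 × ULN, and a creatinine clearance fall ≥ 50% from the pre-first-dose baseline (SAP 3.1.1). Schedule footnote a lets a Protocol 0157 result from the previous 14 days stand for Day 1, so state that this value is then the baseline.
- Add a count of subjects with any post-dose occurrence of each of the five, by dose and overall. Use scheduled and unscheduled results after the first LTS dose through the end-of-study visit, exempt from the latest-result rule. Apply the reporting laboratory's ULN, since protocol Appendix 7 allows local laboratories.
- Footnote that these derived counts may differ from investigator-reported AESIs.
- Record the change in Appendix 1.

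Rows for > 5 ×, > 8 ×, bilirubin and two consecutive results are optional.

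Cost: two criteria in an existing table, one block of 5 rows by 4 columns (20, 80 and 200 mg, overall), one footnote and one line. No protocol change and no new data: AST, ALT and creatinine are in the chemistry panel. Sex and height cancel in the clearance ratio, so a fall ≥ 50% means a creatinine ratio of at least 2 × (140 − current age)/(140 − baseline age). For baseline age 40 that is 2.00 at once, 2 × 99/100 = 1.98 after 1 year and 2 × 97/100 = 1.94 after 3. The drawback is that the derived and reported counts may disagree, which the footnote addresses. If the SAP can no longer be amended, present the counts in the report as an identified modification, as SAP section 1 allows.

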3.4.3.2. Vital Signs

Descriptive statistics for vital signs (heart rate, systolic and diastolic blood pressures, respiratory rate, and body temperature) and changes from baseline values at each visit and at the end of study will be presented by treatment group.

The number and percentage of subjects with marked abnormalities as defined in Table 5 will be summarized and flagged in a listing of all vital signs values.

Table 5: Criteria for Marked Abnormalities in Vital Signs

Heart Rate (bpm)	Systolic Blood Pressure (mm Hg)	Diastolic Blood Pressure (mm Hg)
< 40	< 85	< 45
> 110	> 160	> 100

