**Study Endpoints:**

The primary study endpoint is:

- Incidence and severity of treatment-emergent adverse events, changes in laboratory safety tests, ECGs, and vital sign measurements.

[figure not shown]

[figure not shown]

Additional endpoints are:

- [REDACTED]
- [REDACTED]
- [REDACTED]
- [REDACTED]
- [REDACTED]

[figure not shown]

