### 8.6.4. Vital Signs Data

For each scheduled visit, vital signs summaries will include summary statistics for observed values and changes from baseline. Values above or below the following thresholds will be flagged.

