3.4.3.3. Electrocardiogram

Descriptive statistics for ECG parameters (heart rate, PR interval, QRS interval, QT interval, and QTcF) and changes from baseline values at each assessment time point to the end of study will be presented by treatment group. The QTcF will be calculated using the Fridericia correction.

All recorded values for the standard 12 lead electrocardiogram parameters will be presented in a by-subject listing.

Categorical Analyses

The number and percentage of subjects with absolute ECG values and change from baseline in the ranges shown in Table 6 will be presented in Electrocardiogram Categorical Summary by Visit and Time Point.

Subjects without a postbaseline measurement for a given treatment period will be excluded from the summary statistics (e.g., denominator of the summary statistic) for that time point.

In addition, in the same summary, QTcF will also be summarized by the following categories, Normal (males < 430 , females ≤ 450), Borderline (males $> 430, \leq 450$); females $> 450, \leq 470$) and Prolonged (males > 450 , females > 470).

Individual ECG data collected during the study will be presented in a listing. A separate listing of subjects with values of QTcF > 500 msec or an increase > 60 msec will be provided, as necessary.

Table 6: ECG Interval Categories

Heart Rate (bpm)	Heart Rate Change from Baseline (bpm)	PR Interval (msec)	PR Percentage Change from Baseline (%)	QRS Interval (msec)	QT _c F (msec)	QT _c F change from Baseline (msec)
> 120	≥ 20	≥ 200	≥ 15	≥ 120	Males:	≤ 30
> 130	≥ 30	≥ 220	≥ 25		< 430	>30, ≤ 60
					≥ 430	> 60
					≥ 450	
					≥ 470	
					≥ 480	
					≥ 500	
					Females:	
					< 450	
					≥ 450	
					≥ 470	
					≥ 480	
					≥ 500	

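### The SAP's vital-sign threshold count, and to a lesser extent its QRS category, can mix abnormalities present before the first LTS dose with new ones

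*SAP*

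**What the plan says.** The primary endpoint in the protocol synopsis includes "changes in laboratory safety tests, ECGs, and vital sign measurements".

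For vital signs, Protocol 8.6.4 asks only that "Values above or below the following thresholds will be flagged". SAP 3.4.3.2 goes further and turns the flags into a subject count: "The number and percentage of subjects with marked abnormalities as defined in Table 5 will be summarized". The limits are absolute: heart rate below 40 or above 110 bpm, systolic pressure below 85 or above 160 mm Hg, diastolic pressure below 45 or above 100 mm Hg. The same section also plans descriptive statistics, with "changes from baseline values at each visit and at the end of study will be presented by treatment group", and a listing of every vital-sign value with the abnormal ones flagged.

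For ECGs, SAP 3.4.3.3 tabulates "absolute ECG values and change from baseline in the ranges shown in Table 6", and these "will be presented in Electrocardiogram Categorical Summary by Visit and Time Point". In Table 6, heart rate, PR and QTcF each have absolute and change categories. QRS has one absolute category, 120 msec or more, and no change category. Descriptive changes from baseline and by-subject listings are planned for all ECG parameters, QRS included.

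**The concern.** A count of subjects beyond an absolute limit measures how many were ever abnormal in the readings used. It becomes a count of abnormalities arising during LTS only if the readings are restricted to those after the first dose and baseline status is taken into account. The SAP does neither for Table 5.

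This study has no placebo arm, so a subject's own baseline is the main reference within it. SAP 3.1 also reports safety summaries by treatment, and dose depends on clinical status. Under SAP 1.2 the 20 mg group contains only subjects in remission, while everyone not in remission receives 80 or 200 mg. If baseline heart rate tends to be higher with active disease (an assumption; the documents give no data), a count that disregards baseline could differ by dose without any drug effect.

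**Working it through.** **1. Do the documents restrict the count elsewhere?**

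- SAP 3.1 admits scheduled-visit data to summaries. Day 1 is a scheduled visit, and the notes to the SAP schedule have blood pressure and heart rate taken before dosing at every visit. As written, nothing keeps a pre-dose Day 1 reading out of the Table 5 count.
- SAP 3.1.1 defines baseline as the last pre-dose value, so the information needed for a baseline-aware count exists. SAP 3.4.3.2 does not use it for the threshold count.
- The ECG denominator rule in SAP 3.4.3.3 removes subjects without a post-baseline reading. It does not address subjects already abnormal at baseline.

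**2. Do the entry criteria prevent baseline abnormalities?**

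For laboratory values they largely do. Exclusion 9 (Protocol 4.2) names limits that are stricter than the SAP 3.4.3.1 thresholds:

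| Parameter (×10⁹/L) | Exclusion 9 | SAP count threshold |
|---|---|---|
| Neutrophils | < 1.5 | < 1.0 |
| White cells | < 3 | < 2.0 |
| Lymphocytes | < 0.8 | < 0.5 |

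None of the 12 exclusions gives a number for blood pressure, heart rate or QRS. Exclusion 6 is a judgement about unstable or uncontrolled, clinically significant disease, including cardiovascular disease. Stable hypertension or a chronic wide QRS can pass it.

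**3. How does the SAP treat other safety data?**

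Adverse events before the first dose are classed as not treatment-emergent (SAP 3.4.2). Laboratory data get shifts from baseline relative to normal ranges (SAP 3.4.3.1). The Table 5 count and the QRS category get neither.

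**4. How large could the mixture be?**

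The plan has no figure to reproduce. For illustration, let *p* be the proportion abnormal at LTS baseline, *r* the chance that such a subject is abnormal again after the first dose, and *q* the chance of a new abnormality among those normal at baseline.

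- Count as planned = N·p·r + N·(1 − p)·q
- New since baseline = N·(1 − p)·q, among N·(1 − p) subjects
- Pre-existing share = p·r / [p·r + (1 − p)·q], in which N cancels

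The table uses N = 500, the number anticipated before termination (SAP 1.5); the actual number is not given. All rates are assumed.

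| p | q | r | Pre-existing | New | Planned count | Pre-existing share |
|---|---|---|---|---|---|---|
| 1% | 3% | 0.5 | 2.5 | 14.85 | 17.35 (3.5%) | 14% |
| 3% | 1% | 0.5 | 7.5 | 4.85 | 12.35 (2.5%) | 61% |
| 3% | 1% | 1.0 | 15 | 4.85 | 19.85 (4.0%) | 76% |
| 5% | 1% | 1.0 | 25 | 4.75 | 29.75 (6.0%) | 84% |

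In the second and third rows the new-onset count is about 4.9 of 485 subjects (1.0%). Over p of 1–5%, q of 1–3% and r of 0.5–1, the share runs from 14% to 84%. If Day 1 readings are included, every subject abnormal on Day 1 is counted, so r is 1 by construction. The lower end is then 25% (p = 1%, q = 3%: 0.01 / (0.01 + 0.99 × 0.03) = 0.25).

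**The case against.** A reader might infer that pre-existing abnormalities will be reported as drug findings. The documents do not support that. The SAP calls the Table 5 items marked abnormalities and never labels the counts new, on-drug or treatment-emergent. The count is under-specified rather than mislabelled.

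A reader might also infer that the change component of the endpoint goes unanalysed. It does not: descriptive changes from baseline are planned for every vital sign and for QRS, and all values are listed. What these leave out is how many subjects newly crossed a limit. Means and quartiles do not show that, and the listing shows it only if someone rebuilds it subject by subject.

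For QRS the objection carries more weight. Categories appear by visit and time point, so a stable wide QRS would recur at each visit with changes near zero. The QRS and vital-sign cut-offs also match those in the protocol.

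It would be too strong to say that entry was unrestricted, because exclusion 6 is a partial, qualitative screen and the Protocol 0157 entry limits are not in these documents. SAP 1 also places table specifications in a separate document, which may already restrict the readings or show a baseline row; that cannot be determined here.

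The most important objection concerns the remedy. Many subjects took TD-1473 in Protocol 0157, so an abnormality at LTS baseline precedes LTS but not necessarily the drug. Replacing the count with a new-onset count could hide drug effects. This stands, and it is why the existing count should be kept.

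On dose groups, 80 and 200 mg also hold subjects in remission who continue those doses. Active disease may itself bring more new tachycardia, so a baseline-aware count would not remove confounding by clinical status.

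**Conclusion.** The concern holds in a limited form. The Table 5 count is not tied to post-first-dose readings or to baseline status, and no numeric entry limit keeps baseline abnormalities out, so as specified it can mix pre-existing with new abnormalities. QRS shares the problem to a lesser degree.

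The effect is on the interpretation of a descriptive safety table that bears on a named component of the primary endpoint. No inferential test is planned, and no stated figure changes. The 14% to 84% range shows only that the mixture could be anything from minor to dominant. It rests wholly on assumed rates and should not be read as an estimate for this study. This is a low-cost improvement to a descriptive report of a terminated study.

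**What to change.** In SAP 3.4.3.2:

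- State that the Table 5 count uses readings after the first LTS dose, and whether unscheduled readings qualify. Keep this count for all subjects.
- Beside it, add the count among subjects who did not meet the criterion at LTS baseline, with that group as denominator, labelled *new since LTS baseline*. The label should not suggest that earlier abnormalities were unrelated to TD-1473.
- Add a shift table of baseline by worst post-baseline status for each parameter, with separate rows for the low and high limits and a row for missing baseline.

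In SAP 3.4.3.3, add the same new-since-baseline count and shift table for QRS of 120 msec or more.

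Subjects abnormal at LTS baseline stay in the all-subjects count and appear in the shift table. The full listings remain.

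The cost is a few sentences and some table programming on data already scheduled for collection, with somewhat smaller denominators for the added count. If the table specifications already make this restriction, the SAP needs only to say so. If the tables have been produced, the additions can be supplementary output identified in the study report, as SAP 1 provides for substantive modifications.
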